6.8.1 Loss of contact with participant

If contact is lost with a participant at any point during the trial and they have not explicitly expressed a wish to end their trial participation, the site Research Team will try and establish contact. A minimum of three attempts to contact the participant should be made. If there have been several failed attempts at contacting the participant, it is acceptable to try and re-establish contact at the next follow-up time point. Participants as such can be described as "having lost contact for now".

If the site Research Team is successful in re-establishing contact with the participant, they must ask them to confirm if they wish to continue their participation in the trial. It may be at this point they wish to withdraw, or change their participation status (as detailed in section 6.8).

At the end of the trial, if any participant who lost contact with the trial without explicitly asking to stop participating and for whom no further data was obtained, they are to be described as having been "lost to follow-up".

6.9 Sample collection, transportation, analysis and storage

Obtaining blood samples will be coordinated by the site Research Team. Blood samples will be analysed for serum creatine kinase (CK), and C-reactive protein (CRP) biomarkers pre-operatively and post-operatively at day 0/1 and 6 weeks. The pre-operative samples will be obtained during the participant's routine surgical consenting clinic or pre-operative assessment. The post-operative samples will be obtained whilst the participant is still an inpatient. The 6-week post-operative samples will be obtained during the participants' routine 6-week post-operative surgical review appointment.

All samples will be handled and processed by the local laboratories at the Royal Devon & Exeter Hospital, adhering to all relevant Trust Standard Operating Procedures (SOP) and working instructions.

For participants having their surgery at the NGE, samples will be collected by the clinical staff and couriered back to the RDE for analysis via the routine courier service provided by the Trust.

Blood results will be transcribed from the participant's electronic record into the trial database by the site Research Team.

6.10 Co-enrolment

Any co-enrolment to other research studies will need to be approved by the CI and Co-CI, and the site Research Team.

6.11 End of trial

All participants will be actively followed up until their 12-month (52 week) follow-up and it is at this time point that the participant will complete their involvement in the trial. The end of the trial as a whole will be after all trial participants have completed all follow-ups i.e. when the last participant follow-up at 12 months (52 weeks) post-operative has been completed, no further follow-up is planned, all data queries have been resolved, the database locked, and the analysis completed and the results published. It is at this point that participants and their GP will be sent a notification of treatment allocation letter informing them of which THR technique the participant received.

A declaration of end of trial form will be submitted to the NHS REC who awarded favourable opinion within 90 days of the end of trial.

If the trial is terminated early, the trial will end on the date the Sponsor formally declares the trial terminated in writing. The main NHS REC will be notified of early termination within 15 days of the Sponsor deciding to end the trial.

Term	Definition
Adverse Event (AE)	Any unintentional, unfavourable clinical sign or symptom, or any new illness or disease or the deterioration of existing disease or illness.
Serious Adverse Event (SAE)	 An SAE is considered to be any event that leads to Death Serious deterioration in the health of the participant that results in: life-threatening illness or injury; permanent impairment of a body structure or function; in-patient hospitalisation or prolongation of existing hospitalisation; medical or surgical intervention to prevent life-threatening illness or injury or permanent impairment to a body structure or a body function Chronic disease Other important medical events' may also be considered serious if they jeopardise the participant or require an intervention to prevent one of the above consequences. NOTE: The term "life-threatening" in the definition of "serious" refers to an event in which the participant was at risk of death at the time of the event; it does not refer to an event which hypothetically might have caused death if it were more severe.
Related and Unexpected SAE (RUSAE)	A related and unexpected SAE is an event that is related to the intervention, and 'unexpected' – that is, the type of event is not listed in the protocol as an expected occurrence.

7 SAFETY REPORTING

7.1 General definitions

7.2 Operational Definitions

The safety reporting flowchart in section 7.3.1 summarises the safety reporting process.

7.2.1 Adverse Events (AE)

AEs should be recorded from the point of surgery to the end of trial participation.

Not all non-serious AEs need to be recorded or reported, as described in the following sections.

7.2.2 Non-reportable adverse events

Some events which occur during treatment and recovery will be considered normal aspects of the anaesthetic and post-operative recovery process, and that occur frequently after surgery. They will not need reporting as AEs, unless in the opinion of the CI are untoward, excessive, or outside of what might normally be expected for the procedure, or fall into the category of an SAE. These include:

- Nausea and/or vomiting after surgery
- Drowsiness or headache after surgery
- Temporary low blood pressure after surgery
- Sore throat after surgery
- Itching after surgery
- Post-operative pain (note that this will be collected as an outcome) unless this is considered abnormal by the treating clinical team
- Memory loss or confusion during the hospital stay only, or which the treating clinician believes is due to analgesics
- Numbness on the lateral side of the surgical wound
- Early wound oozing which spontaneously resolves
- Bruising, unless this is considered abnormal by the treating clinical team
- Mild discomfort during or immediately after physiotherapy (inpatient and outpatient).

7.2.3 Reportable adverse events

Some events will be considered reportable expected AEs (or SAEs, if they meet the criteria). In certain cases, the diagnoses will be confirmed, where there is uncertainty, by the treating clinician. These include:

Those related in general to surgery and anaesthetic (within 6 weeks of surgery):

- Urinary retention
- Chest infection
- Myocardial infarction
- Stroke
- Nerve or vessel injury due to local anaesthetic (i.e. local blocks or spinal anaesthetic)
- Spinal haematoma.

Those related to the operation itself (within 12 weeks of surgery):

- Infection
- Wound healing problems
- Fracture of the bone around the hip replacement
- Implant failure, dislocation, or loosening
- Revision surgery or other corrective surgery
- Thrombosis (deep vein thrombosis, pulmonary embolus, cerebral infarct)
- Damage to nerves or vessels in the surgical area
- Persistent muscle soreness or muscle injury
- Bruising
- Haematoma

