- To compare differences between (i) PSPA vs PA and (ii) SPAIRE vs PA in terms of pain medication used in addition to the standardised prescribed post-surgery medication, immediately post-surgery and 6 week post-operatively.
- To evaluate safety of PSPA and SPAIRE approaches with respect to the PA via recorded adverse events from the day of surgery until 12 months (52 weeks) post-operatively via medical notes and post-operative follow-up at 6 weeks, 6 months (26 weeks), and 12 months (52 weeks).

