7.3 Reporting adverse events

All reportable AEs/SAEs/RUSAEs should be recorded from the point of surgery to the end of trial participation at 12 months (52 weeks) follow-up post-operatively.

SAEs must be reported directly onto REDCap **within 24 hours** of the blinded site Research Team becoming aware of the event. SAEs classed as possibly, probably or definitely related AND unexpected (RUSAEs) will be reported by ExeCTU to the Sponsor within 24 hours of ExeCTU staff becoming aware. The Sponsor is responsible for onward reporting of RUSAEs to the REC within 15 days of the event being reported to ExeCTU in REDCap. However, if the event results in death the SAE will be reported to the REC within 7 days of the event being reported to ExeCTU in REDCap.

The CI (in their role as site PI) or their delegate, is responsible for signing off reportable SAEs within the EDC system. This will be a role restricted task that only authorised users of the EDC can complete.

For each SAE the following information will be collected:

- full details in medical terms and case description
- event duration (start and end dates, if applicable)
- action taken
- outcome
- seriousness criteria
- causality (i.e. relatedness to intervention)

Any change of condition or other follow-up information should be updated directly onto REDCap as soon as it is available. Events will be followed up until the event has resolved or a final outcome has been reached. An outcome of 'unknown' is not considered to be an acceptable final outcome. An outcome of 'not yet resolved' is an acceptable final outcome for non-serious AEs at the end of a participant's involvement in a trial, and for SAEs at database lock.

Where SAE causality is initially assessed by an authorised delegate of the CI but not the CI themselves, the CI (in their role as CI, as opposed to site PI) will record a second assessment of causal relationship. The CI may upgrade the causality assessment (e.g. from not related to related) but may not downgrade the assessment (e.g. related to not related). Where a causal relationship is suggested, the CI will record an assessment of expectedness.

The TSC and DMC will periodically review SAE data to determine patterns and trends of events, or to identify safety issues, which would not be apparent on an individual case basis.

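### The 6- and 12-week limits on reportable events do not fit a safety objective that runs to 52 weeks, and the protocol does not say whether they limit recording or only expectedness

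*Protocol*

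**What the plan says.** The safety objective in section 3.2 compares PSPA and SPAIRE with PA "via recorded adverse events from the day of surgery until 12 months (52 weeks) post-operatively". The endpoint table in 3.5 gives the same period, and the trial summary names related adverse events alongside serious ones, so non-serious related events are in scope.

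Section 7.2.1 opens with a general rule, "AEs should be recorded from the point of surgery to the end of trial participation", and then qualifies it: "Not all non-serious AEs need to be recorded or reported, as described in the following sections". Two sections follow. Section 7.2.2 lists events that need no report. Section 7.2.3 begins "Some events will be considered reportable expected AEs (or SAEs, if they meet the criteria") and gives two lists, each with a time limit:

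- "Those related in general to surgery and anaesthetic (within 6 weeks of surgery"): for example chest infection, stroke and urinary retention.
- "Those related to the operation itself (within 12 weeks of surgery"): for example infection, fracture, dislocation, loosening, revision, nerve damage, and persistent muscle soreness or injury.

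Section 7.3 then states: "All reportable AEs/SAEs/RUSAEs should be recorded from the point of surgery to the end of trial participation at 12 months (52 weeks) follow-up post-operatively". Sections 6.7.7 and 6.7.8 ask staff to report AEs and SAEs and to document additional surgery for weeks 6 to 26 and 26 to 52. The notes review at those two contacts is for SAEs.

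**The concern.** The same event carries two windows. Suppose a participant mentions at the 26-week call a non-serious muscle injury that arose in week 16. Section 6.7.7 tells staff to report it. Section 7.3 asks for reportable events to 52 weeks, but the section that says what is reportable attaches a 12-week limit to that event. The protocol does not tell the site whether to enter it.

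Two things are at stake. The first is the record behind the 52-week objective. The background section motivates the trial partly by lasting effects of tendon release, citing external rotation weakness still present at 12 months, so late non-serious muscle problems bear on the question. Because the late notes review covers SAEs only, such events reach the database through participant contact and each staff member's reading of 7.2.3. That invites uneven recording, and events never entered are hard to recover.

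The second is expectedness. Section 7.2.3 labels its events both reportable and expected. If the time limit is part of that label, a related serious complication could follow one reporting route inside the window and another outside it.

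**Working it through.** The protocol gives no figure of its own to reproduce. The check sets the windows side by side and then does simple arithmetic on weeks.

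**Windows by type of event**

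| Event | Collected to | Source |
|---|---|---|
| Deaths | 12 months | 7.4 |
| SAEs | 52 weeks | 7.3; 6.7.7; 6.7.8 |
| Additional surgery | 52 weeks | 6.7.7; 6.7.8 |
| Non-serious, operation-related list | 52 weeks by 6.7.7, 6.7.8 and 7.3; 12 weeks if 7.2.3 is a cut-off | conflict |
| Non-serious, general surgical and anaesthetic list | 52 weeks by 6.7.7, 6.7.8 and 7.3; 6 weeks if 7.2.3 is a cut-off | conflict |

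**Step 1: does anything settle the conflict?** Section 7.3 does not, because it applies to reportable events and 7.2.3 is where reportable events are listed with limits. Section 7.2.1 does not, because its general rule yields to the sections that follow it. The late contacts ask for AEs without mentioning either window.

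**Step 2: size, if the limits are reporting cut-offs.** Uncovered share = (52 − limit) / 52.

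- Operation-related list: (52 − 12) / 52 = 40 / 52 = 77%; covered 12 / 52 = 23%.
- General list: (52 − 6) / 52 = 46 / 52 = 88%; covered 6 / 52 = 12%.

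These are shares of calendar time for non-serious listed events only. If the limits govern expectedness only, the uncovered share is 0 for both lists. The protocol gives no rates or timing for these events, so no number of lost events can be derived.

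**Step 3: expectedness.** The definitions table in section 7 calls a serious event unexpected when its type is not listed as an expected occurrence. Dislocation is a listed type, but it is listed under a 12-week limit. For a related dislocation that meets the SAE criteria in week 13 there are two readings:

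- by type alone, it is expected and is not a RUSAE;
- by type and window, it is unexpected and is a RUSAE, which under 7.3 goes to the Sponsor within 24 hours and to the REC within 15 days.

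Nothing in the protocol chooses between them.

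**Step 4: effect on the planned table.** Section 8.9 describes SAEs only, by treatment received. SAEs are collected to 52 weeks, so the gap takes nothing out of that table. It affects the wider adverse-event objective in the summary, 3.2 and 3.5.

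**The case against.** The strongest case against is that 7.2.3 is not a cut-off at all. Its lists are illustrative and are labelled as expected events, so 6 and 12 weeks read naturally as the periods in which such events are to be expected. The section that excludes events is 7.2.2, and that alone could satisfy the qualification in 7.2.1. The schedule of events marks AE and SAE reporting at both late contacts. The safety flowchart in 7.3.1 is not visible in the text reviewed and may show how later events are handled. OHS, LEFS and EQ-5D-5L at 26 and 52 weeks also pick up late pain and function.

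Much of this stands. The expectedness reading is plausible and may be what was meant. But the section is headed as being about reportable events, and its wording never says that the limits concern expectedness alone. If they do not limit reporting, their purpose should be stated.

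A reader might go further and infer two things that the protocol does not support:

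- **That most of the safety window is uncovered.** Serious events, deaths and additional surgery are collected to 52 weeks regardless of the lists. Hospitalisation, or intervention to prevent permanent impairment, makes an event serious, so many important late complications are captured.
- **That a related serious dislocation after week 12 counts as unexpected.** The definition turns on event type, so this is one reading of two. Even on that reading the result is faster reporting, not lost data.

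**Conclusion.** The inconsistency is real but narrow. It leaves two matters open: whether non-serious listed events are recorded after week 6 or week 12, and whether a listed event type outside its window is still expected. The first spans 46 or 40 of the 52 weeks, but only on the assumption that the limits are reporting cut-offs, which the text permits without requiring. The planned SAE table is unaffected. The exposure is that a site reading 7.2.3 as a cut-off would leave out non-serious events that the 52-week objective needs, and could do so unevenly. The point merits correction because the remedy is cheap.

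**What to change.** Reconcile 7.2.1, 7.2.3, 7.3, 6.7.7, 6.7.8 and the safety objective by stating two rules separately.

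1. **Recording.** State that listed operation-related events, non-serious ones included, are recorded to the 52-week contact, as the objective requires. Say explicitly what applies to the general surgical and anaesthetic list.
2. **Expectedness.** State whether the 6- and 12-week windows govern expectedness only, and hence how a related SAE of a listed type is classified after its window.

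The rules should not be merged. Simply extending the existing lists to 52 weeks would also widen what counts as expected, and could take late related SAEs out of expedited reporting without anyone having decided that.

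If non-serious recording is in fact meant to stop at 6 or 12 weeks, restate the safety objective in the summary, 3.2 and 3.5 to say so, and align the instructions for the late contacts.

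The cost is protocol wording, an eCRF instruction, and a few more adverse-event entries at contacts that already take place.

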7.2.4 Causality

Causality of reportable SAEs will be assessed by the CI (in their role as site PI) or authorised delegate), see table 2. All SAEs which are possibly, probably or definitely related to the intervention will be categorised as 'related'. If the CI or delegate is unable to assign causality within 24 hours of the site becoming aware of the event, the SAE will be treated cautiously and subjected to expedited reporting (see section 7.3 below).

Table 2: The causality of SAEs (i.e. relationship to trial treatment) will be assessed by the site PI (or delegate) using these descriptions:

Relationship to trial procedure	Description
Unrelated	There is no evidence of any causal relationship
Unlikely to be related	There is little evidence to suggest there is a causal relationship (e.g. the event did not occur within a reasonable time after administration of the trial intervention). There is another reasonable explanation for the event (e.g. the participant's clinical condition, other concomitant treatment)
Possible relationship	There is some evidence to suggest a causal relationship (e.g. because the event occurs within a reasonable time after administration of the trial intervention). However, the influence of other factors may have contributed to the event (e.g. the participant's clinical condition, other concomitant treatments)
Probable relationship	There is evidence to suggest a causal relationship and the influence of other factors is unlikely
Definitely related	There is clear evidence to suggest a causal relationship and other possible contributing factors can be ruled out

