Secondary objectives	To compare differences between SPAIRE, PSPA, and PA in terms of muscle damage and global inflammation using serum creatine kinase (CK), and C-reactive protein (CRP) blood biomarkers pre-operatively and post-operatively at day 0/1 and 6 weeks.
	To compare differences between SPAIRE, PSPA, and PA in terms of length of hospital stay, duration of surgery, and blood loss.
	To investigate potential mechanisms of action of the three forms of surgery in terms of their effect on OARS, using mediation analysis with CK and CRP as mediators of OARS.
	To compare differences between SPAIRE, PSPA, and PA in terms of participant walking (daily steps, step rate, and walking bout time), and sleep parameters (daily sleep time, and sleep quality) measured via an activity monitor worn for 2 weeks at pre-operative assessment, and post-operatively at 6 weeks, 6 months (26 weeks), and 12 months (52 weeks).
	To compare differences between SPAIRE, PSPA, and PA in terms of PROMs (Oxford Hip Score, Lower Extremity Function Scale, EuroQol 5D-5L, and Self-Administered Patient Satisfaction) pre-operatively, and post-operatively at 6 weeks, 6 months (26 weeks), and 12 months (52 weeks).

To compare differences between SPAIRE, PSPA, and PA in terms of additional analgesic use from immediately post-surgery up to 6-weeks post-operatively.
To use the post-operative follow-ups at 6 weeks, 6 months (26 weeks) and 12 months (52 weeks) to compare the trajectory of outcome measures between the three groups and evaluate whether there are any differences in outcomes over time across the groups.
To evaluate safety of PSPA and SPAIRE, by reporting related adverse events and serious adverse events.

TRIAL FLOWCHART

FUNDING AND SUPPORT IN KIND

FUNDER	FINANCIAL SUPPORT GIVEN
NIHR Efficacy and Mechanism Evaluation	£916,086.21
(EME)	£942,352.21 (including NHS Support Costs)

ROLE OF THE TRIAL SPONSOR, FUNDER, AND CLINICAL TRIALS UNIT

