To compare differences between PSPA and PA, and SPAIRE and PA in terms of pain medication used in addition to the standardised prescribed post-surgery medication, immediately post- surgery and 6 weeks post- operatively	 Additional over-the-counter or prescribed analgesia needed during the first 6 weeks post- operative? (Yes/No and list any additional medication) 	6 weeks post-operatively
To evaluate the safety of PSPA and SPAIRE approaches with respect to the PA	Adverse events recorded from the day of surgery	Until 12 months (52 weeks) post-operatively via medical notes and post-operative follow- up at 6 weeks, 6 months (26 weeks), and 12 months (52 weeks)

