6.7 Trial assessments

6.7.1 Schedule of events

	Time point								
	Pre-op			Post-op					
Assessment/visit	Screening	Pre-op assessment (baseline)	7 days prior to surgery (Research Team)	24 hours prior to surgery (Surgeon & theatre staff)	Day 0/1 (inpatient)	Notes review after discharge	6 weeks (+/- 2 weeks)	6 months (26 weeks) (-4 weeks/+12 weeks)	12 months (52 weeks) (-4 weeks/+12 weeks)
Check eligibility and provide PIS	Х								
Confirm inclusion/exclusion criteria		Х							
Consent		Х							
Demographic data (name, DOB, sex of patient, height, weight, BMI, ethnicity), any existing comorbidities, and contact details		X							
Blood biomarkers – CK and CRP		Х			Х		Х		
Activity monitor issued in clinic and prepaid returns envelope provided		X					X		
PROMs – OHS, LEFS, EQ-5D-5L in clinic		Х							
Randomisation			Х	Х					
Check pre-operative imaging has been requested by surgeon (imaging to be done within 3 months of surgery date)		X							
Peri-operative data: length of stay ¹ , surgery time, blood loss, conversion of allocated randomisation approach ²						X			
PROMs – OARS, OACS, OHS, LEFS, EQ-5D-5L, SAPS in clinic							X		
Activity monitor issued via post and prepaid returns envelope provided								Х	Х
PROMs – OHS, LEFS, EQ-5D-5L, SAPS remotely								Х	Х
Additional analgesia use							Х		
Safety reporting – AEs and SAEs					Х	Х	Х	X	Х
Additional surgical procedures								X	Х
¹ Length of stay is recorded at time of discharge, i.e. converted to another during surgery (SPAIRE to PS	number of n PA or PA; or	ights a participa PSPA to PA).	int stays in	hospital post-	surgery. ² Co	nversion of a	pproach recor	ds if the intende	ed approach is

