8.9 Adverse events analyses

SAEs will be reported descriptively by treatment as received (with footnotes to indicate where treatment received was not as allocated).

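### Section 8.9 analyses SAEs only, although the safety objective is a comparison with PA on all recorded adverse events

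*Protocol*

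**What the plan says.** **Objective and outcome measure.** The trial summary gives the aim as "To evaluate safety of PSPA and SPAIRE, by reporting related adverse events and serious adverse events". Section 3.2 makes it comparative and does not mention relatedness: "To evaluate safety of PSPA and SPAIRE approaches with respect to the PA via recorded adverse events from the day of surgery". Table 3.5 gives the outcome measure as "Adverse events recorded from the day of surgery", followed to 12 months.

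**Collection.** The schedule of events (6.7.1) has a row for "Safety reporting – AEs and SAEs", marked at every post-operative column. Section 7.2.1 allows some selection: "Not all non-serious AEs need to be recorded or reported". Section 7.2.2 then lists the normal post-operative events that need not be reported. Section 7.2.3 lists those that are reportable, whether or not they meet an SAE criterion. Section 7.3 has reportable AEs and SAEs recorded from surgery to the 12-month follow-up.

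**Causality.** Section 7.2.4 states: "Causality of reportable SAEs will be assessed by the CI". In 7.3 the data items, including relatedness, come under the words "For each SAE the following information will be collected".

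**Analysis.** Section 8.9 is headed as the adverse events analysis and consists of one sentence: "SAEs will be reported descriptively by treatment as received", with footnotes where the treatment received differs from the allocation. Deaths have their own summary in 8.6.1.

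**The concern.** The objective, the outcome measure and the collection rules all cover adverse events. The analysis section covers only the serious ones. An analyst who follows 8.9 would summarise SAEs and stop there, and the non-serious reportable events would be collected but have no stated place in the results.

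This matters because of what the trial is about. The rationale in section 1 is less musculo-tendinous damage. Sections 5.4 and 5.5 say that the tendon-sparing approaches limit access and visibility compared with PA. Several events in 7.2.3 bear directly on that trade-off: muscle soreness or injury, nerve or vessel damage, wound healing problems and haematoma. Each can occur without meeting an SAE criterion. A safety conclusion drawn from SAEs alone would rest on part of the evidence gathered for it.

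**Working it through.** No figure in the Protocol is in dispute, so the check is a comparison of the relevant sections.

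| Step | Where | Events covered | Relatedness |
|---|---|---|---|
| Objective, summary | Trial summary | AEs and SAEs | Mentioned |
| Objective, main text | 3.2 | Recorded AEs, compared with PA | Not mentioned |
| Outcome measure | Table 3.5 | Recorded AEs | Not mentioned |
| Collection | 6.7.1, 7.2.3, 7.3 | Reportable AEs and SAEs, to 12 months | See next row |
| Causality | 7.2.4, 7.3 | SAEs | Specified for SAEs |
| Analysis | 8.9 | SAEs | No analysis specified |

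1. **Analysis against objective.** Section 3.2 and table 3.5 cover all recorded AEs. Section 8.9 covers SAEs. The set in 8.9 is therefore narrower, and the part left out is the reportable non-serious AEs.
2. **Whether the omitted part is collected.** It is. Section 7.2.3 lists 6 event types linked to surgery and anaesthesia in general (within 6 weeks) and 10 linked to the operation itself (within 12 weeks), so 6 + 10 = 16 types. Its opening sentence treats them as AEs that become SAEs only if they meet the criteria. Non-serious occurrences are therefore expected in the database.
3. **Whether causality restricts the comparison.** It does not. A comparison of event proportions between randomised arms needs the event and the arm, not a judgement of relatedness. Sections 7.2.4 and 7.3 therefore take nothing out of the comparison in 3.2; the restriction comes from 8.9.
4. **Whether the summary objective can be met as worded.** Only in part. Individual relatedness is specified for SAEs, so the Protocol specifies no event-level assessment by which non-serious AEs could be reported as related. Of the three statements of the objective, only the summary has this problem.
5. **Size.** The Protocol gives no expected AE or SAE rate in any arm. Any count of omitted participants would rest on an invented rate, so none is given.

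**The case against.** **The general reporting rule.** Section 8.4 says that all outcomes will be reported descriptively, and table 3.5 lists adverse events as an outcome measure. On that reading non-serious AEs would be tabulated anyway, and 8.9 would only set the as-received rule for SAEs. This has some force: the Protocol nowhere says that non-serious AEs are excluded. But 8.9 is the specific section, carries the general heading and names only SAEs. Section 3.4, which sets out the secondary outcomes, does not include adverse events. Two analysts could defend different reports, so 8.4 does not settle the matter.

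**The SAP.** Table layouts and event-level summaries are commonly left to the SAP, and their absence here is no fault. That stands for the detail. It does not answer the mismatch, because 8.9 states a scope that is narrower than the objective, and a SAP written to follow it would carry that scope forward.

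**A stronger reading about causality.** A reader might infer that non-serious harms drop out because causality is assessed for SAEs only. The documents do not support this. Case-by-case causality serves the expedited reporting of related and unexpected SAEs in 7.3, and limiting it to SAEs is coherent for that purpose.

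**A stronger reading about identification.** A reader might also infer that related non-serious AEs can never be identified. That goes too far. The headings in 7.2.3 group events by their relation to surgery or to the operation, with time windows, and the summary's wording could be read that way. Those headings classify event types, however; they are not an assessment of an individual event on the scale in Table 2. The non-serious AE form is not shown, so it cannot be said to lack a relatedness field.

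**Other evidence on tissue effects.** CK, CRP and additional surgical procedures are also recorded. They inform the question but do not replace a comparison of the adverse events themselves.

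**Conclusion.** The point holds as a mismatch between a stated analysis and a stated objective. Section 8.9 provides for SAEs; the objective and outcome measure cover all recorded AEs; the non-serious reportable events among 16 listed types fall between the two. The difference between the summary's wording and the SAE-only causality rule is a separate and smaller inconsistency.

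The conclusion assumes that 8.9 is followed as written and that 8.4 is not read to override it. It makes no claim that the arms differ in non-serious events, or that a report would wrongly declare them equally safe: 8.9 plans description and no test. One secondary objective is affected. The primary outcome, its analysis and the sample size are not. The correction should be made, because it is cheap and the safety objective lacks a matching analysis without it.

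**What to change.** **Section 8.9.** Extend it to reportable AEs as well as SAEs, by arm:

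- the number and percentage of participants with at least one reportable AE;
- counts by event type, using the 7.2.3 list;
- a risk difference with 95% CI for PSPA vs PA and for SPAIRE vs PA, on the at-least-one summary only. Intervals for each of the 16 types would be mostly sparse and are not needed.

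Settle this before the trial team is unblinded.

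**Relatedness.** Choose one of two routes. Dropping the word related from the summary objective brings it into line with 3.2 and table 3.5 and needs no data. Alternatively, collect relatedness for non-serious reportable AEs and amend 7.2.4 and 7.3 to say so. The second route adds a form item and assessment time. For events already recorded it may be hard to carry out, because 7.3 specifies a case description only for SAEs.

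**Cost.** The change to 8.9 uses data already being collected and adds one or two tables.
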